An important aspect of gastric emptying and physiology is GMA which reflects the gastric pacemaker activity that coordinates gastric peristaltic contractions. The GMA is measured with electrogastrography methods that will be used in this study.

Electrogastrography is a non-invasive method of recording GMA that is used to diagnose gastric dysrhythmias in patients with intractable chronic nausea and vomiting, gastroparesis and gastroesophageal reflux (15,16,17). Electrogastrography signals are recorded using standard EKG-type electrodes placed on the surface of the upper stomach. 3CPM Company developed the first patented, non-invasive FDA-approved diagnostic device that records and displays the EGG signal and provides analysis of the GMA signal for clinical diagnosis.

Gastric dysrhythmias (tachygastria, 3.7 to 10 cpm, bradygastria, 1.0-2.5 cpm) and mixed dysrhythmias (combinations of tachygastria and bradygastria) are recorded with electrogastrography (17,18,19). In addition, patients with gastroparesis may have normal (2.5 to 3.7 cpm) or hypernormal GMA. These patients have antro-pyloro-duodenal

outflow dysfunction and respond well to endoscopic or surgical therapies (20). The pattern(s) of GMA in response to the WLST in obese patients who will undergo BE procedures is unknown. In addition, the volume of water ingested in 5 minutes during the WLST indicates gastric capacity or accommodation which may be an important variable in patient selection for BE. Finally, in patients with functional dyspepsia or gastroparesis, symptoms induced by the WLST include nausea, fullness, bloating and pain and are scored on a VAS. These symptoms, if elicited in the obese patients, may also represent an important variable for patient selection (21, 22, 23).

The position of the electrodes on the upper abdominal surface, skin preparation and test meals influence the GMA recordings. Interestingly, neither age nor sex has a definitive impact on the parameters for in adults or children (24, 25, 26).

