Controversial findings on the correlation between EGG and GE have been reported in the literature. Different authors have said that a normal 3 cpm GMA may not predict normal GE and dysrhythmic GMA may be present in delayed GE but is also present in functional dyspepsia. Patients with delayed GE and abnormal EGG have more severe symptoms and more tachygastria in pre and post-prandial states than patients with normal GE. 80% of the non-obese population has normal EGG and 20% have variability (27, 28, 29, 30). There is only one preliminary study of GMA with WLST before BE techniques in obesity (31), but has not been studied in before and after BE procedures to determine subtypes of GMA and whether or not subtypes will predict successful bariatric outcomes.

Therefore, we propose a study to evaluate the GMA in response to the WLST in patients who have agreed to BE procedures. We hypothesize that GMA patterns in response to the WLST, the volume of water ingested and the array of symptoms elicited will help to predict successful outcomes of the bariatric procedures and thus help with patient selection for these procedures.

2.- WORKING HYPOTHESIS

Weight loss and long-term maintenance may be conditioned by changes in GMA, as well as by anatomical modifications induced by the bariatric procedure.

Since anatomical modifications of the stomach by the BE procedures are related to weight loss, our purpose is to determine whether different procedures to reduce gastric capacity will result in substantial changes in GMA and in the water load volume ingested. No studies that have studied obese population before and after such BE procedures are available.

Therefore, an important question is whether obese patients have the GMA that is similar to those with functional dyspepsia and normal weight (32). Also, the usefulness of electrogastrography as a new tool to customize choice of Bariatric therapies by determining success or failure based on GMA and WLST results has not been studied. GMA measures the normal or depleted gastric ICCs and the WLST measures gastric capacity, objective measures that may be important to predict success of Bariatric procedures and thus to help with patient selection to maximize efficacy and minimize side effects (32).

Hypothesis Question: Pre-intervention EGG can predict clinical success and adverse events after bariatric interventions?.

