Demonstrate the usefulness of EGG measuring the GMA by identifying subtypes with the Water Load Satiety Test (WLST) in obese adults to predict individual successful responses to BE treatments: Intra-gastric Balloon (IGB) placement and Apollo Endoscopic Sleeve Gastroplasty (ESG) method.

Demonstrate the usefulness of EGG measuring the GMA by identifying subtypes with the Water Load Satiety Test (WLST) in obese adults to predict individual successful responses to BE treatments: Intra-gastric Balloon (IGB) placement and Apollo Endoscopic Sleeve Gastroplasty (ESG) method

3.- OBJECTIVES

3.1.- Primary Objective –

- . Pre-intervention EGG parameters and/or changes in EGG parameters (one/three months) after bariatric intervention can predict clinical success at the end of follow up
- a. Pre-intervention EGG parameters and/or changes in EGG parameters after the bariatric intervention can predict adverse events at the end of follow-up.

3.2. Secondary:

- a. Secondary Objective
To predict suitable bariatric intervention for patients depending upon a pre-intervention EGG.
- b. EGG is a feasible diagnostic tool in obese population with reproducible and predictable results

4.- STUDY DESIGN AND METHODOLOGY

4.1. Type of study: Multicenter, prospective, observational study in patients with body mass index (BMI) at 30 kg/m² prior and after one, and three, six and 12 months of a bariatric procedure. All tests will be analyzed by one blinded specialist.

4.2. Study design: This is a pilot study, involving 2 hospitals in Spain and India, where 4 groups of patients will be recruited.

- a) Group of 50 patients who will undergo BIG placement
- b) Group of 50 patients who will undergo Endoscopic Sleeve Gastroplasty (ESG) Apollo method.
- c) Group of 50 patients who will undergo Surgical Sleeve Gastrectomy (SEG) Apollo method

d) Group of 50 patients who will undergo RYGB method

The protocol will be carried out in the run-up to the BE procedure until 12 months after of follow up. As a control group, 50 people (of the same age and gender) will be selected, with BMI less than 25% who voluntarily agree to participate in the protocol and have the same criteria of inclusion or exclusion of patients that belongs to all the groups, except BMI.

Duration – 18 months to 24 months

4.3. Characteristics of subjects:

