4.4. Collection of data and variables to be studied

Anamnesis: Collection of clinical data in the medical history: history of obesity, evolution of weight, associated comorbidities, personal and family history. Dietary history.

Anthropometric data: Weight, size, waist circumference, BMI.

Electrogastrography data: clinical diagnosis, percentage distribution, ratios

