****The total volume of water consumed will be recorded.***

4.7. EGG signal analysis

EGG signal is reviewed for movement artifacts. Artifact – free minutes are chosen for blinded computer analysis (at baseline, three, six and 12 months recordings and for each type of BE procedure). The selected minutes of EGG are analyzed by spectral analysis

by computer applications. 3CPM EGGSAS GMAT Threshold software will be used for signal analysis. EGG data will be organized by clinical diagnosis. Water load volumes ingested that are <238 ml are considered abnormally low (33).

5.- STATISTIC

The normal distribution of the variables will be confirmed by the kolmogorov-Smirnoff test. Quantitative variables shall be expressed as mean s/e d or means (interquartile range). Comparison between groups will be performed by parametric or nonparametric tests, depending on the distribution of the variables. Spearman or Pearson correlation will be used for the study of correlations. The possibility of multivariate logistic regression analysis will be explored. An SPSS statistical programme will be used. EGG data will be descriptive in terms of overall clinical EGG diagnosis and normal or abnormal water load volume ingested. Symptom data before and after the WLST will be tabulated. These measures will be calculated before and 3 and 6 months after the BE procedures.

6.- STUDY LIMITATIONS

Recruitment of the number of subjects should not be a problem due to the high number of patients performed in the different centers and will allow the selection of those with the most approximate clinical results between groups.

A strength of the study is to have a control group of non-obese subjects, which will allow us to know the normal pattern of GMA in response to the WLST and whether it is similar to those worldwide reported in healthy individuals.

All tests will be carried out by the same expert operator in the medical center and analyzed by one specialist in EGG that received the blinded information from all the centers because it is a multicenter study, but the bariatric procedures will be performed by different operators from every center.

7.- STAGES OF DEVELOPMENT AND DISTRIBUTION OF THE AREAS OF ALL RESEARCH EQUIPMENT

The clinical study will be conducted simultaneously in AIG hospitals, Hyderabad, India, and Gastrodex, Dexeus University Hospital center in Spain. The task layout of the study team members will be as follows:

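### The committed analyses are unadjusted, so an association that only reflects water volume, procedure or body size could be reported as showing that EGG is useful

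*Protocol*

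**What the plan says.** The aim, placed just before Section 3, is to "Demonstrate the usefulness of EGG measuring the GMA by identifying subtypes with the Water Load Satiety Test (WLST) in obese adults" so as to predict individual response. Section 3.1 then names EGG alone, once for efficacy, "Pre-intervention EGG parameters and/or changes in EGG parameters (one/three months) after bariatric intervention can predict clinical success at the end of follow up", and once for safety, "Pre-intervention EGG parameters and/or changes in EGG parameters after the bariatric intervention can predict adverse events at the end of follow-up".

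Section 1.3 is broader. It says that "the volume of water ingested in 5 minutes during the WLST indicates gastric capacity or accommodation which may be an important variable in patient selection", and its closing paragraph puts all three forward as predictors of success: "We hypothesize that GMA patterns in response to the WLST, the volume of water ingested and the array of symptoms elicited will help to predict". Volume and symptoms are thus candidate predictors from the same session as the EGG.

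The data for an adjusted analysis are collected. Section 4.4 lists "Anthropometric data: Weight, size, waist circumference, BMI" as well as comorbidities, and the recording procedure requires the volume drunk to be noted.

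On analysis, Section 5 plans group comparisons by parametric or nonparametric tests with no adjustment stated. It adds "Spearman or Pearson correlation will be used for the study of correlations" and descriptive summaries of EGG diagnosis and of normal or abnormal volume. It then says that a multivariate logistic regression may be explored, without naming an outcome, predictors or a comparison of models with and without EGG.

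**The concern.** Whether an EGG device is useful depends on what it tells the clinician beyond what is already known: the procedure, the patient's size and the amount of water drunk. A marginal correlation between EGG and outcome does not answer that.

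The protocol's own text gives three routes by which EGG could borrow its association:

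- **Water volume.** Patients drink until full, so the load differs between them, and the 30-minute recording follows that load. Section 1.3 also says that test meals affect the recording. This route applies mainly to post-water recordings.
- **Procedure.** Section 2 expects the procedures to change GMA, and expects their anatomical effect to drive weight loss. If procedures are pooled, a change in EGG and the outcome can move together for that reason alone.
- **Body size.** Excess weight loss in Table 1 has initial minus ideal weight as its denominator, so baseline weight enters the outcome by construction.

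An analysis that followed Section 5 to the letter could report a pairwise correlation as meeting the primary objective although EGG adds nothing.

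**Working it through.** The protocol states no alpha, power, effect size or expected success rate, only 50 patients in each of four procedure groups (4 × 50 = 200). There is therefore no figure of its own to reproduce. What follows is an illustration of the water-volume route.

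**Assumptions, none from the documents:** two-sided alpha 0.05; EGG-volume correlation ρ from 0.3 to 0.7; volume-outcome correlation b from 0.3 to 0.5, or an odds ratio of 2 to 3 per SD of volume; 70% success at mean volume; EGG has no effect once volume is known.

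**Step 1, correlation test.** If EGG acts only through its link with volume, its marginal correlation with outcome is r = ρ × b. The chance of significance is Φ(t − 1.96) + Φ(−t − 1.96), with t = atanh(r) × √(n − 3).

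Example: ρ = 0.5 and b = 0.5 give r = 0.25. At n = 50, t = 0.2554 × 6.856 = 1.75, and the chance is Φ(−0.21) plus a negligible term, 41.7%.

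| b | ρ | r | n=50 | n=200 |
|---|---|---|---|---|
| 0.3 | 0.3 | 0.09 | 9.5% | 24.5% |
| 0.3 | 0.5 | 0.15 | 17.9% | 56.4% |
| 0.3 | 0.7 | 0.21 | 30.9% | 84.9% |
| 0.5 | 0.3 | 0.15 | 17.9% | 56.4% |
| 0.5 | 0.5 | 0.25 | 41.7% | 94.8% |
| 0.5 | 0.7 | 0.35 | 70.7% | 99.9% |

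**Step 2, binary outcome.** Section 1.3 defines failure by a threshold, so logistic models were also simulated, 2,000 runs per setting. Likelihood-ratio tests were made of EGG alone and of EGG added to volume.

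| Odds ratio | ρ | n=50 alone | n=50 added | n=200 alone | n=200 added |
|---|---|---|---|---|---|
| 2 | 0.3 | 9.6% | 6.7% | 24.0% | 5.7% |
| 2 | 0.5 | 17.9% | 5.2% | 55.2% | 6.0% |
| 2 | 0.7 | 31.9% | 5.9% | 83.7% | 4.8% |
| 3 | 0.3 | 15.2% | 5.7% | 44.4% | 5.3% |
| 3 | 0.5 | 33.3% | 5.6% | 86.0% | 5.6% |
| 3 | 0.7 | 56.6% | 5.4% | 99.2% | 5.5% |

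The simulation standard error near 5% is √(0.05 × 0.95 / 2000), about 0.5 percentage points. In every setting EGG alone is significant more often than 5%, and adding volume brings the rate back to about 5-7%.

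**The case against.** A reader might infer that the plan never tests EGG on top of other data. The document does not support that. Section 5 leaves multivariable logistic regression open, and a statistical analysis plan that is not shown may contain it. What stands is narrower: the analyses the protocol commits to do not answer its stated aim, and the one that could is optional and unspecified.

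A second objection is that water volume may be no rival at all. The title joins GMA and the water load test, and the end of Section 1.3 lists patterns, volume and symptoms together. On that reading volume is part of the test under study. This is fair, but Section 3.1 names EGG alone, so the text is at best ambiguous and should be settled.

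Third, the percentages are not false positives for the bare statement that EGG can predict. In the scenario EGG does correlate with outcome. They are errors only if the result is read as value of EGG itself, which is how the aim is worded.

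Fourth, the 15-minute baseline recording precedes the water, so that session's load cannot have altered it. The load mechanism therefore does not reach that recording. Procedure and body size can still matter.

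Finally, covariate lists usually belong in an analysis plan, and a long one would suit a pilot badly. Procedure (3 terms), BMI, age, sex, comorbidity, volume, five symptom scales and EGG make 14 parameters. That argues for a short model, but does not rescue unadjusted tests as evidence for the aim.

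**Conclusion.** The point holds as a weakness of the stated analysis, not as proof that the added value of EGG will go untested. Following Section 5 as written, EGG could be credited with what water volume, procedure or body size explains.

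The size is uncertain because the documents give no EGG-volume or volume-outcome correlation. Over the assumed range, an EGG measure that adds nothing is significant without adjustment in about 10-71% of trials at n=50 and 25-99.9% at n=200. The logistic middle case (ρ = 0.5, odds ratio 2) gives 18% and 55%, against about 5-7% with volume in the model. No single value from these ranges should be quoted as the error rate of this study. The n=200 figures also assume that all four procedures are pooled, which the protocol does not state.

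The change is worth making because it needs no new measurement.

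**What to change.** Replace the optional regression in Section 5 with a short pre-specified nested comparison on the same patients:

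1. Procedure, baseline BMI and water volume in ml.
2. The same, plus one pre-specified EGG parameter.

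Base any claim that EGG itself is useful on step 2. Report the likelihood-ratio test and the change in AUC (or R-squared for a continuous outcome) with its 95% CI, and label the result exploratory because the study is a pilot. If the intended index test is EGG and water load together, say so and make the claim for the combined test, not for EGG.

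This comparison addresses prognosis only. The secondary objective of predicting a suitable procedure from the pre-intervention EGG would need an EGG-by-procedure interaction.

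Cost: wording, a few degrees of freedom and a harder test for EGG. With four procedures pooled, step 2 has 3 + 1 + 1 + 1 = 6 slopes. If 30% of 200 failed, that is 60 failures, or 60 / 6 = 10 per slope. Failures may be fewer, since Section 1.3 cites mean excess weight loss of at least 50% at six months after ESG, which is a further reason to keep the model this short.

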Voluntary patients with obesity will be recruited among those patients who will be given any of the four types of bariatric procedures described above, at the time before and after the first, third, sixth and 12 months of performing the bariatric methods.

Patients will be recruited in AIG Hospitals, Gachibowli, Hyderabad

Inclusion criteria:

1. Men and women, aged between 18-65 yrs
2. IMC basal ≥ 30 kg/m²
3. Patient undergoing bariatric intervention willing to participate in the study
4. Informed consent (oral and written) for the tests to be carried out.

Exclusion criteria:

1. Presence of severe cardiac, renal, hepatic, or neurological disease
2. Long term use of medication that alter gastric motility (> 4 weeks)
3. Significant alcohol or opioids or narcotics or tobacco
4. Active malignancy
5. Pregnancy
6. Uncontrolled Diabetes Mellitus with glycosylated hemoglobin (HbA1c) levels $\geq 6.5\%$ or glucose level more than 270 mg/dL.
7. Uncontrolled hypothyroidism (High TSH with low levels of Free T4)

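### The protocol is inconsistent on whether patients are recruited at one hospital or two, and controls are not matched on site, so country could be mixed up with obesity status and, if both hospitals recruit, with procedure

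*Protocol*

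**What the plan says.** Three places in the protocol bear on where patients come from.

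- Section 4.2 (study design): "This is a pilot study, involving 2 hospitals in Spain and India, where 4 groups of patients will be recruited".
- Section 4.3 (characteristics of subjects): "Patients will be recruited in AIG Hospitals, Gachibowli, Hyderabad". No other hospital is named there.
- Section 7 (stages of development): "The clinical study will be conducted simultaneously in AIG hospitals, Hyderabad, India, and Gastrodex, Dexeus University Hospital center in Spain".

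Section 4.2 fixes four procedure groups of equal size, the first being "Group of 50 patients who will undergo BIG placement", and gives no number per hospital for any of them. On controls it says "As a control group, 50 people (of the same age and gender) will be selected", and that they must "have the same criteria of inclusion or exclusion of patients that belongs to all the groups, except BMI". It does not say at which hospital controls are found.

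Section 6 adds that "the bariatric procedures will be performed by different operators from every center". Reading of the recordings is central: "All tests will be analyzed by one blinded specialist" (section 4.1).

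**The concern.** Site stands for several things at once: the population, the local operator and the local choice of procedure. Section 1.3 itself says that electrode placement, preparation of the skin and the test meal affect the recording. If groups under comparison differ in their country mix, a difference in gastric myoelectrical activity, water volume, weight loss or adverse events may reflect country rather than obesity or procedure.

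Two uses of the data are exposed. Section 6 presents the control group as a strength because it supplies the normal pattern, and section 2 asks how obese patients compare with people of normal weight. Secondary objective (a) is to choose a suitable procedure from the baseline EGG, which means weighing response under one procedure against response under another. Adjustment for site in the analysis works only where the groups overlap across sites. Where group and site coincide, no analysis can separate them, so the recruitment and matching rules belong in the protocol.

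**Working it through.** **1. Where patients are recruited.** Section 4.2 has two hospitals and four recruited groups. Section 7 has both hospitals working at the same time. Section 6 bases its confidence about recruitment on patient volume in the different centres. Section 4.3 names Hyderabad alone. No sentence explains the difference.

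**2. What each reading implies.**

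- Hyderabad alone recruits patients: procedure cannot be confounded with country. Obese versus control can be, if any controls come from Spain.
- Both hospitals recruit: obese versus control can be confounded with country, and so can procedure, because no split by site is set.

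**3. Is an uneven mix plausible?** Section 1.2 gives national shares of bariatric operations: in Spain, gastric bypass 43% and sleeve 34%; in India in 2018, sleeve 48% and RYGB 15%. Assume equal surgical volume at the two hospitals, recruitment in proportion to these shares, and that the Spanish bypass figure is RYGB. Then India supplies:

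- sleeve group: 48 / (48 + 34) = 48/82 = 59%
- RYGB group: 15 / (15 + 43) = 15/58 = 26%

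The gap in country mix is about 33 points. This illustrates the mechanism and does not forecast these two hospitals.

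**4. How much it could matter.** The protocol gives no figure to reproduce here beyond group sizes: 4 × 50 = 200 patients, plus 50 controls = 250. For illustration, take 20% abnormal EGG in one country (section 1.3 gives 20% with variability in non-obese people), a rate higher by d in the other (assumed 5 to 20 points), and no true group effect. With s the difference in country mix between two groups:

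- bias in the abnormal rate = s × d
- false-positive rate = Φ((D − 1.96·se0)/se1) + Φ((−D − 1.96·se0)/se1), with D = s × d, se0 the pooled and se1 the unpooled standard error, two-sided 5%.

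Worked case, controls (50) versus patients (200), s = 1, d = 10 points: rates 0.20 and 0.30; pooled rate (10 + 60)/250 = 0.28; se0 = √(0.28 × 0.72 × (1/50 + 1/200)) = 0.0710; se1 = √(0.16/50 + 0.21/200) = 0.0652; (0.10 − 0.1391)/0.0652 = −0.60, which gives 27%. The second term is negligible.

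For partial separation the shares are set at (1 − s)/2 and (1 + s)/2.

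| Comparison | Mix difference s | d = 5 | d = 10 | d = 15 | d = 20 |
|---|---|---|---|---|---|
| Controls 50 v patients 200 | 25 points | 5% | 6% | 8% | 10% |
| | 50 points | 6% | 10% | 17% | 26% |
| | complete | 10% | 27% | 53% | 78% |
| Procedure 50 v 50 | 25 points | 5% | 6% | 7% | 8% |
| | 50 points | 6% | 9% | 13% | 19% |
| | complete | 9% | 21% | 39% | 59% |

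A 33-point gap, as in step 3, lies between the 25- and 50-point rows: about 6% to 9% at d = 10 and 8% to 19% at d = 20, with a bias of 0.33 × 10 = 3.3 points or 0.33 × 20 = 6.6 points.

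**5. After the fix.** With equal country mix in the groups compared, s = 0. The bias is then 0 and the false-positive rate is the nominal 5%, whatever d is.

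**The case against.** A reader might infer from section 4.3 that none of the 200 patients will be Spanish. The protocol does not support that. Section 4.3 does not exclude a second site, and sections 4.2, 6 and 7 all point to two recruiting centres, so an incomplete site line is the likelier explanation. A reader might also infer that country is confounded with procedure and with control status together, by design. Confounding with procedure arises only if both hospitals recruit, and nowhere does the protocol place controls in Spain or confine a procedure to one hospital. The task list introduced in section 7 is not in the text available to me and might assign work by site.

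There are also real safeguards: one blinded reader, one named device and software (sections 4.5 and 4.7), and a scripted instruction for the water load to be used identically at each site. The primary objective is prediction from each patient's own EGG, secondary objective (a) is not worded as a head-to-head comparison, and obese versus control is not a listed objective. Site adjustment where sites overlap may properly sit in an SAP.

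Most of this stands, and it limits the point to a risk. It does not remove the contradiction. The safeguards narrow differences in recording and reading but leave population, operator and procedure mix. An SAP cannot repair a control group drawn from the wrong site.

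**Conclusion.** The contradiction over recruiting sites is plain on the text and must be reconciled. The control rule is too weak for a two-country study, since it fixes age and gender and leaves site open. The consequence is a possible confounding with country, not a demonstrated or planned one. It bears mainly on the control comparison and secondary objective (a). The primary objective is less exposed, although a model pooled over hospitals could still carry a site effect.

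The size depends on two quantities the protocol does not give: the country difference in the outcome and the difference in country mix. Under the assumptions shown, partial imbalance inflates false positives modestly, and complete separation does so severely. The largest figures (78% and 59%) need both complete separation and a 20-point country difference, and should not be read as expected values. This should be changed, but it does not undermine the study as a whole.

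**What to change.** 1. Correct section 4.3 to name both recruiting hospitals. If only Hyderabad recruits, remove the two-country description from sections 4.2 and 7 instead.
2. In section 4.2, match controls on recruiting site as well as age and gender, in proportion to each site's patients. With 50 controls for 200 patients that is one control for every four patients at each hospital.
3. Make any comparison between procedures within site or stratified by site, and state as a limitation any procedure group that comes from one site only.

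The cost is protocol wording and control recruitment split between the hospitals. I would not go further and require every procedure to contribute from both hospitals, or exclude single-site procedures from comparison. For an observational pilot that is a debatable trade-off, and an open statement of the limitation is enough.
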